8. NUMBER OF SUBJECTS

- *Indicate the total number of subjects to be accrued locally. If applicable, distinguish between the number of subjects who are expected to be pre-screened, enrolled (consent obtained), randomized and complete the research procedures.*
- *If your study includes different cohorts, include the total number of subjects in each cohort.*
- *If this is multisite study, include total number of subjects across all sites.*

There is an expected number of 80 recruited subjects from all aforementioned sites (Northwell Health Division of Nephrology, Division of Endocrinology, and Winthrop University Hospital Division of Nephrology).
We expect all patients will complete the research procedures

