10. ENDPOINTS

- *Describe the primary and secondary study endpoints*
- *Describe any primary or secondary safety endpoints*

- Primary End-Points: 1) Correlation between HbA1c and mean glucose concentration measured by CGM; 2) Characterization of hypoglycemic events, number, severity and duration. (Also, a safety end-point).
- Secondary End-Points: 1) Correlation between serum fructosamine and mean glucose concentration measured by CGM, 2) Determination of HbA1c and serum fructosamine regression equation, slope, Y intercept, average glucose at different test levels, 3) Number of hyperglycemic events and duration of each hyperglycemic event, 4) Study glucose variability as measured by mean amplitude of glucose excursion

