- The FreeStyle Libre Pro Flash Glucose Monitoring System is a professional continuous glucose monitoring (CGM) device indicated for detecting trends and tracking patterns in persons (age 18 and older) with diabetes. The Freestyle Libre Pro device is FDA approved (PMA# P150021). Participants will use the FreeStyle Libre Pro Flash Glucose Monitoring device according to its approved use, on the back of the arm.
- CGM monitoring will be performed on Day 1 by placing the Freestyle Libre Pro on research subjects for intended use of 14 days.
- Subjects will be advised to return to the research site on Day 14 to remove the CGM device for analysis. On Day 14, blood will be drawn for HbA1c and fructosamine, funded by internal research funds and there will be no charge to the patient. The blood drawn for this research will be approximately 10-15 milliliters.
- There are no drug washout periods. Subjects will continue to take all their medications and/or insulins as prescribed by their doctor.
- Baseline data including age, race, ethnicity, past medical history, home medication list, and diabetes related laboratory data will be collected from Allscripts medical records. No personal identifying information will be collected.

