12. STATISTICAL ANALYSIS

- *Describe how your data will be used to test the hypotheses.*
- *State clearly what variables will be tested and what statistical tests will be used.*
- *Include sample size calculations.*
- *If this is a pilot study, state which variables will be examined for hypothesis generation in later studies.*

Patients with less than 7 days of CGM measurements will be excluded from analysis. Arithmetic mean glucose (AMG) will be calculated for each patient from

all CGM glucose measurements. A simple linear regression model will be applied to estimate the relationship between AMG and HbA1c. Once the relationship is established through the model, prediction of mean AMG together with 95% confidence intervals will be calculated at different levels of HbA1c. Influence of factors such as age, gender on the relationship between HbA1c and AMG will be examined through a multivariate regression model. Slopes and intercepts of the regression equations for the individual subgroups will be compared to those of the simple linear regression model. A quadratic regression model will also be applied if the relationship between the two variables is not linear. The same analysis will be performed to establish the relationship between AMG and serum fructosamine. Linear and quadratic regression models will be applied to estimate the relationship between AMG and HbA1c and serum fructosamine. If a linear relationship is established then slope, Y-intercept and correlation coefficient will be calculated. Mean AMG at different levels of HbA1c and serum fructosamine will be calculated. Glucose variability will be calculated as MAGE scores. First all the local maximum/minimum values are determined. The next step is an assessment of maximum/minimum pairs against the standard deviation (SD). If the difference from minimum to maximum is greater than the SD, this variation from mean measure is retained. If the local maximum/minimum is less than 1 SD it is excluded from further calculations. These troughs are retained and summed to achieve the MAGE score.

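### The MAGE rule sums the retained excursions and never divides by their number, so the score is not the mean amplitude named as the endpoint

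*Combined protocol and SAP*

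**What the plan says.** The fourth secondary endpoint in section 10 is "Study glucose variability as measured by mean amplitude of glucose excursion". Section 12 takes this up: "Glucose variability will be calculated as MAGE scores".

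The algorithm in section 12 first finds the local maxima and minima, then compares each pair with the standard deviation:

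- Retention: "If the difference from minimum to maximum is greater than the SD, this variation from mean measure is retained".
- Exclusion: "If the local maximum/minimum is less than 1 SD it is excluded from further calculations".
- Final step: "These troughs are retained and summed to achieve the MAGE score".

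That final step closes the section. Neither section 12 nor any other section divides by the number of retained excursions or by the days of record.

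Three statements bear on record length. Section 12 sets the minimum: "Patients with less than 7 days of CGM measurements will be excluded from analysis"; section 16 repeats it. Section 11 gives the intended wear: "placing the Freestyle Libre Pro on research subjects for intended use of 14 days". Section 8 adds: "We expect all patients will complete the research procedures".

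**The concern.** A sum is not a mean. Section 10 asks for a typical excursion size, and section 12 produces a running total that grows with every further excursion. Two patients with the same glucose pattern get different scores if one sensor recorded for longer. Two patients with equal wear can be ranked in the wrong order if one has many modest excursions and the other has fewer large ones.

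Section 4 makes glucose variability one of the six study goals, and MAGE is the only measure specified for it. If MAGE is computed as written, no other planned analysis answers that goal. An analyst who codes section 12 literally and one who follows the endpoint name in section 10 would report numbers that differ by a factor equal to the excursion count.

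**Working it through.** The plan states no MAGE value, and no sample size or test depends on one, so there is no figure to reproduce. The check applies the written rule and compares it with the divided version.

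**Inputs from the document:** minimum record 7 days (section 12); intended wear 14 days (section 11); threshold 1 SD; aggregation by summing.

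**Assumed inputs:** excursion rate and amplitude. The document gives neither, nor a distribution of wear time.

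**Identity.** Let n be the number of retained excursions, A their mean amplitude, r the retained excursions per day and d the days of record.

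- Score as written = n × A = r × d × A
- Mean amplitude = (n × A) / n = A

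**Wear time.** At constant r and A, the ratio of 14-day to 7-day scores is 14/7 = 2.00, whatever r and A are. With r = 3 per day and A = 60 mg/dL:

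| Days | Sum as written | Sum / n |
|---|---|---|
| 7 | 3 × 7 × 60 = 1260 | 60 |
| 10 | 3 × 10 × 60 = 1800 | 60 |
| 14 | 3 × 14 × 60 = 2520 | 60 |

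Excursions of 120 mg/dL over 7 days also give 3 × 7 × 120 = 2520. Twice the amplitude over half the wear cannot be told apart from the 14-day row.

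**Excursion count at full 14-day wear.**

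- 60 mg/dL, 4 per day: 60 × 4 × 14 = 3360
- 100 mg/dL, 2 per day: 100 × 2 × 14 = 2800

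The patient with the smaller excursions scores higher.

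**Simulation with the 1 SD filter applied.** Traces were at 15-minute intervals, with baseline 150 mg/dL and autoregressive noise of SD 6. Rises were kept if larger than 1 SD of the trace. Each cell had 60 traces, with rises of 40, 60, 80 or 120 mg/dL at 1 to 5 per day. Over these 20 amplitude-by-rate settings the 14-day to 7-day ratio was 1.97 to 2.07 for the sum and 0.99 to 1.04 for the mean. At 60 mg/dL and 3 per day:

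| Days | Count | Sum | Mean (mg/dL) |
|---|---|---|---|
| 7 | 20.5 | 1368 | 66.8 |
| 10 | 29.0 | 1952 | 67.2 |
| 14 | 40.8 | 2748 | 67.4 |

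With 14-day wear and 60 mg/dL rises:

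| Rises per day | Sum | Mean (mg/dL) |
|---|---|---|
| 2 | 1985 | 70.7 |
| 3 | 2748 | 67.4 |
| 4 | 3498 | 64.5 |
| 5 | 4275 | 63.8 |

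From 2 to 5 rises per day the sum grows 4275/1985 = 2.15-fold while the mean falls slightly.

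**Second simulation, different trace model.** This used three meal peaks a day of about 70 mg/dL (SD 25), with 500 records per duration. Average sums were 1189, 1731 and 2461 at 7, 10 and 14 days, against means of 65.7, 66.0 and 66.1 mg/dL. In 2000 records with wear spread evenly over 7 to 14 days, the correlation with days worn was about 0.95 for the sum and 0.01 for the mean.

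**The case against.** The best reply is that this is a dropped last step in a loosely drafted paragraph. The endpoint name in section 10 and the label MAGE both point to a mean, and other words in the same paragraph (troughs, for example) already have to be read generously. That may well be what happened. But no section supplies the missing division, and summing is the one operation the plan states explicitly. A slip of this kind still has to be corrected before someone programs it.

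Second, MAGE is the last of four secondary endpoints, and section 12 applies no test, regression or cutoff to it. This stands, and it limits the consequence to a descriptive result. The stated hypotheses concern HbA1c and hypoglycemia.

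Third, the 2-fold figure compares the shortest analysable record with full wear, while section 8 expects everyone to complete. This also stands: the typical wear-time effect is unknown and may be small. If placement on Day 1 and removal on Day 14 are counted as 13 elapsed days, the ratio is 13/7 = 1.86, although section 2 speaks of 14 consecutive days. Neither point touches the dependence on excursion count.

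Fourth, all amplitudes and rates are assumed. They illustrate the identity and do not estimate an effect in this trial.

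Fifth, the paragraph does not say whether the SD is per day or over the whole record, and it is loose about direction. Corrected wording has to settle both. A per-patient SD and a minimum-to-maximum amplitude are the natural readings.

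**Conclusion.** The concern holds. Followed literally, section 12 computes excursion count times mean amplitude, which is not the endpoint in section 10. The identity and the conflict between the two sections rest on no outside figure; they take the troughs in section 12 to mean the retained minimum-to-maximum amplitudes. The 2-fold wear-time spread needs only a constant excursion rate and the plan's own 7- and 14-day limits. The absolute scores, the 2.15-fold effect of count and the reversal of 3360 against 2800 rest on assumed rates and amplitudes.

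It should be fixed, because the plan's only variability measure is computed as a different quantity. It does not threaten the primary endpoints or the sample size.

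**What to change.** Replace the last two sentences of section 12 with:

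> Minimum-to-maximum differences not exceeding 1 SD of that patient's CGM readings are excluded. MAGE is the sum of the retained minimum-to-maximum amplitudes divided by the number of retained excursions.

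This keeps the 1 SD threshold and the minimum-to-maximum difference. The sentence just before should be aligned, so that what is retained is the minimum-to-maximum difference and not a variation from the mean. If the investigators intend a per-day SD, they should say so; the division is needed either way.

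The cost is two replaced sentences and a small wording alignment. No new data are needed and no other analysis changes.

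### The MAGE derivation in section 12 does not yield the mean excursion amplitude that section 10 names as secondary endpoint 4

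*Combined protocol and SAP*

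**What the plan says.** Section 10 lists as the fourth secondary endpoint: "Study glucose variability as measured by mean amplitude of glucose excursion". Section 12 says "Glucose variability will be calculated as MAGE scores" and then gives the only derivation in the document, in five sentences:

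1. "First all the local maximum/minimum values are determined".
2. "The next step is an assessment of maximum/minimum pairs against the standard deviation (SD").
3. "If the difference from minimum to maximum is greater than the SD, this variation from mean measure is retained".
4. "If the local maximum/minimum is less than 1 SD it is excluded from further calculations".
5. "These troughs are retained and summed to achieve the MAGE score".

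The same section sets the minimum wear: "Patients with less than 7 days of CGM measurements will be excluded from analysis". Intended wear is 14 days (section 11), so analysed records can run from 7 to 14 days.

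**The concern.** The object of the calculation changes from sentence to sentence. Sentence 3 tests a difference between two glucose values, but what it keeps is described as a variation from the mean. Sentence 4 names an extremum rather than a difference. Sentence 5 adds up troughs, a word not used before, and is the only sentence that says what enters the score. No sentence divides by the number of excursions, although the endpoint is a mean.

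Two analysts following section 12 could therefore compute different scores from one trace, and neither would have the quantity in section 10. At stake is goal 6 in section 4 (glucose variability) and secondary endpoint 4, for which these sentences are the whole specification.

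**Working it through.** **Inputs.** The documents give the rule, the 7-day minimum and the 14-day intended wear. They give no MAGE value, glucose distribution or sampling interval, so there is no planned figure to reproduce. All glucose values below are assumptions: smooth traces sampled every 15 minutes, three swings a day.

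**Formulas.** Let k be the number of rises whose minimum-to-maximum difference exceeds the patient's SD.
- T = sum of the k trough glucose values (troughs read as low glucose values).
- S = sum of the k differences (troughs read as retained differences).
- D = sum of the k distances from the mean down to the trough (troughs read as retained variations from the mean).
- M = S / k, the endpoint in section 10.

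**Fixed traces.** A 14-day record gives k = 41 complete rises.

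| Trace (mg/dL) | M | T | S | D |
|---|---|---|---|---|
| A: 100 to 200, mean 150 | 100 | 41 × 100 = 4,100 | 41 × 100 = 4,100 | 41 × 50 = 2,050 |
| B: 60 to 240, mean 150 | 180 | 41 × 60 = 2,460 | 41 × 180 = 7,380 | 41 × 90 = 3,690 |
| C: 150 to 250, mean 200 | 100 | 41 × 150 = 6,150 | 41 × 100 = 4,100 | 41 × 50 = 2,050 |

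B swings 80% more than A (180/100), yet T is 40% lower (2,460/4,100 = 0.60). C swings exactly as much as A, yet T is 50% higher (6,150/4,100 = 1.50). S and D order A, B and C correctly. B alone scores 2,460, 7,380 or 3,690 depending on the reading.

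**Dependence on wear time.** A 7-day record gives k = 20. For trace A, S is 20 × 100 = 2,000 at 7 days and 4,100 at 14 days, a ratio of 2.05, while M is 100 at both. T and D grow in the same proportion.

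**Dependence on swing frequency.** With an amplitude of about 80 mg/dL and 14 days, S is 2,159, 3,265 and 5,494 at 2, 3 and 5 swings a day. M stays at about 80.

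**Simulated groups of 80.** Assumptions: mean glucose 160 mg/dL, within-patient CV uniform on 18 to 42%, 2.5 to 4.5 swings a day, 14 days for everyone.

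| Between-patient SD of mean glucose (mg/dL) | Correlation of T with true amplitude |
|---|---|
| 0 | -0.71 |
| 20 | -0.33 |
| 35 | +0.04 |
| 50 | +0.27 |

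Over the same range S correlates about +0.81 to +0.90 with true amplitude. In this setup amplitude scales with mean glucose. A second set of traces drew amplitude independently of the mean. There the rank correlation of T with mean amplitude was -1.00 at equal means and -0.45 at a between-patient SD of 40. In that second set S gave +0.95 at a fixed 14 days, falling to +0.84 when wear varied from 7 to 14 days.

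**The case against.** The strongest reply is that the intended rule can be recovered. Section 12 names the metric MAGE, section 10 spells it out, and sentences 2 and 3 set the right screen. Sentence 5 says the troughs are retained, and the only item already described as retained is the variation in sentence 3. On that reading the differences or deviations are summed and patients are not ranked backwards. This stands as far as it goes: *troughs* is not defined as a glucose level, so the text is ambiguous. It does not rescue the rule, because a sum is still not a mean.

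A reader might infer that the plan will report the most variable patients as the least variable. The documents do not support that as a general statement. It requires reading troughs as glucose values and also assuming that patients have similar mean glucose. The study regresses mean glucose on HbA1c, so it expects means to differ, and even the sign of the correlation then depends on the assumed traces.

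A reader might also infer from sentence 4 that glucose levels are to be screened against the SD, which would delete very low troughs. In trace B the trough of 60 lies below the SD of 180/(2√2) = 63.6, so a literal screen would remove every trough. That case is narrow: about 2 to 3% of simulated patients had troughs below 1 SD. The sentence also reads naturally as the converse of sentence 3 with the word for the pair left out. It needs tidying, but the point does not rest on it.

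Finally, the impact is limited. Neither hypothesis in section 4 concerns variability, and MAGE can be recomputed from the CGM readings. That limits the weight of the point without removing the mismatch.

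**Conclusion.** The point holds as a mismatch between endpoint and derivation. Under each reading examined, the written score differs from the endpoint in section 10. With low glucose values summed, it is not a measure of amplitude. It runs in reverse at similar means (about -0.7) and is unrelated or weakly positive at widely varying means if amplitude scales with the mean. With differences summed, the ordering is broadly right, but the score about doubles from 7 to 14 days of wear and rises with the number of swings.

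The missing division and the change of object follow from the text alone. The sizes rest on assumed traces. The consequences stop at secondary endpoint 4 and goal 6. Both primary endpoints, the correlation of HbA1c with mean glucose and the hypoglycemia description, are untouched. The correction should be made before the variability analysis is run.

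**What to change.** Replace the last three sentences of section 12 with:

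> For each local minimum-maximum pair, the amplitude is the difference between the two glucose values. Pairs whose amplitude is 1 SD or less are excluded, where SD is that of the patient's own CGM glucose values. MAGE is the arithmetic mean of the retained amplitudes (their sum divided by their number).

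This removes the references to variation from the mean and to troughs, applies the 1-SD screen to the difference only, and makes scores comparable between patients with different lengths of wear. Both parts are needed: dividing a sum of trough values by their number would give a mean trough glucose, and naming the difference without saying *mean* would still allow a total.

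Cost: wording only, with no new data, patients or procedures.

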13. SPECIMEN BANKING

- *If specimens will be banked for future research, describe where the specimens will be stored, how long they will be stored, how they will be accessed and who will have access to the specimens*
- *List the information that will be stored with each specimen, including how specimens are labeled/coded*
- *Describe the procedures to release the specimens, including: the process to request release, approvals required for release, who can obtain the specimens, and the information to be provided with the specimens.*

N/A

14. DATA MANAGEMENT AND CONFIDENTIALITY

- *Describe the data and specimens to be sent out or received. As applicable, describe:*
 - *What information will be included in that data or associated with the specimens?*
 - *Where and how data and specimens will be stored?*
 - *How long the data will be stored?*
 - *Who will have access to the data?*
 - *Who is responsible for receipt or transmission of data and specimens?*
- *Describe the steps that will be taken to secure the data during storage, use and transmission.*

The above data will be stored using Red Cap.

Access to study data will be limited to IRB approved personnel.

Data will be stored according to Northwell Health retention of records policy GR052.

Data received from sites external to Northwell Health will be de-identified, with the link to identity maintained by the home site.

Northwell participant PHI will not be disclosed to any external participating site.

15. DATA AND SAFETY MONITORING PLAN

A specific data and safety monitoring plan is only required for greater than minimal risk research. For guidance on creating this plan, please see the [Guidance Document](#) on the HRPP website.

Part I – this part should be completed for all studies that require a DSMP.

Part II – This part should be completed when your study needs a Data and Safety Monitoring Board or Committee (DSMB/C) as part of your Data and Safety Monitoring Plan.

Part I: Elements of the Data and Safety Monitoring Plan

- *Indicate who will perform the data and safety monitoring for this study.*
- *Justify your choice of monitor, in terms of assessed risk to the research subject's health and well being. In studies where the monitor is independent of the study staff, indicate the individual's credentials, relationship to the PI, and rationale for selection*
- *List the specific items that will be monitored for safety (e.g. adverse events, protocol compliance, etc)*
- *Indicate the frequency at which accumulated safety and data information (items listed in # above) will be reviewed by the monitor (s) or the DSMB/C.*
- *Where applicable, describe rules which will guide interruption or alteration of the study design.*
- *Where applicable, indicate dose selection procedures that will be used to minimize toxicity.*
- *Should a temporary or permanent suspension of your study occur, in addition to the IRB, indicate to whom will you report the occurrence.*

Not applicable

Part II: Data and Safety Monitoring Board or Committee

- *When appropriate, attach a description of the DSMB.*
- *Provide the number of members and area of professional expertise.*

- *Provide confirmation that the members of the board are all independent of the study.*

N/A

16. WITHDRAWAL OF SUBJECTS

- *Describe anticipated circumstances under which subjects will be withdrawn from the research without their consent*
- *Describe procedures for orderly termination*
- *Describe procedures that will be followed when subjects withdraw from the research, including partial withdrawal from procedures with continued data collection.*

During the monitoring phase, the diabetes medications will not be changed unless indicated by their private endocrinologist or internist, in which case the patient will be withdrawn from the study for fulfilling an exclusion criterion. Furthermore, patients with less than 7 days of CGM measurements will be excluded from statistical analysis due to limited data collection.
--

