7. ELIGIBILITY CRITERIA

- *Describe the characteristics of the subject population, including their anticipated number, age, ranges, sex, ethnic background, and health status. Identify the criteria for inclusion or exclusion of any subpopulation.*
- *Explain the rationale for the involvement of special classes of subjects, such as fetuses, pregnant women, children, prisoners or other institutionalized individuals, or others who are likely to be vulnerable. You cannot include these populations in your research, unless you indicate such in the protocol*
- *Similarly, detail exclusionary criteria: age limits, special populations (minors, pregnant women, decisionally impaired), use of concomitant medications, subjects with other diseases, severity of illness, etc.*

- We anticipate recruiting 80 subjects for this study. We anticipate a fair distribution of males and females, Caucasians, African Americans, and people from other ethnic groups. We anticipate that most patients in this age group are relatively healthy with possibly 1-5 past medical health problems.
- Inclusion Criteria: patients who are 18 years and older with the ability to speak and understand English and with T2DM AND CKD stages 3b-5. Vulnerable populations would include elderly and minorities, as listed in section 26 below for vulnerable populations. There are minimal risks of participating in this study for all subjects including vulnerable populations.
- Exclusion criteria: patients with Type I DM, ESRD on HD, hemoglobinopathies, who have received red blood cell transfusions in the last 12 weeks, with hemoglobin <9, current use of acetaminophen on a daily basis, steroid treatment in the prior 12 weeks, greater than 50% change in diabetes medications or new diabetes medications started in the prior 12 weeks, patients who are currently pregnant.

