19. POTENTIAL BENEFIT TO SUBJECTS

- *Explain what benefits might be derived from participation in the study, noting in particular the benefit over standard treatment (e.g. a once-a-day administration instead of four times a day, an oral formulation over an IV administration).*
- *Also state if there are no known benefits to subjects, but detail the value of knowledge to be gained*

The CGM data analysis can be provided to subject's endocrinologist if requested by the subject at the end of their participation. The subject's endocrinologist may make medication or insulin adjustments based on the CGM data which may be beneficial to the patient.

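### Withdrawal for any diabetes-medication change, together with a 7-day CGM minimum applied to all analysis, lets inclusion in the primary and safety hypoglycemia endpoint depend on the outcome

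*Combined protocol and SAP*

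**What the plan says.** Section 10 makes hypoglycemia the second primary endpoint, and labels it a safety endpoint too: "Characterization of hypoglycemic events, number, severity and duration".

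Two rules govern who contributes to it.

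- **Medication change.** Section 16 allows the patient's own physician to change diabetes medication during monitoring, "in which case the patient will be withdrawn from the study for fulfilling an exclusion criterion". No size of change is specified.
- **Short wear.** Section 12 opens with "Patients with less than 7 days of CGM measurements will be excluded from analysis", before any model is named. Section 16 repeats it: "patients with less than 7 days of CGM measurements will be excluded from statistical analysis due to limited data collection". Neither sentence ties the rule to a particular endpoint.

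Section 12 then describes regressions of mean glucose on HbA1c and fructosamine, and a glucose-variability score. It gives hypoglycemia no analysis set of its own. The form's prompt in Section 16 asks for procedures at withdrawal, "including partial withdrawal from procedures with continued data collection"; the answer does not take this up. Section 8 plans 80 subjects and expects all of them to complete.

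The criterion in Section 7 to which Section 16 appears to refer is narrower: "greater than 50% change in diabetes medications or new diabetes medications started in the prior 12 weeks".

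**The concern.** A stable regimen and adequate wear are sensible conditions for relating HbA1c to mean glucose. They are not needed to describe hypoglycemia in patients who, under Section 11, stay on their usual prescribed treatment. Here the same rules reach both endpoints.

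Low or high glucose is an obvious reason for a physician to change diabetes medication. A change removes the patient, so presence in the hypoglycemia data can be decided by hypoglycemia itself. The endpoint is descriptive and has no test attached, so the estimate is the result. Section 4 expects the incidence to be high. If the set of patients behind the estimate is selected on glycemia, the confidence interval will not show it. The plan also asks for no account of exclusions by reason from which a reader could judge it.

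**Working it through.** **1. Who is lost, from the text.** The plan states no rate or calculation to reproduce.

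- *Change in days 1-6:* withdrawn under Section 16. If withdrawal ends the study's CGM record, fewer than 7 days exist and the patient is out of all analysis. This exclusion follows from the stated rules.
- *Change on day 7 or later:* withdrawn, but the 7-day minimum may be met. The plan is silent on whether the readings are used.
- *Short wear with no glycemic cause (for example a sensor falling off):* excluded, but this costs precision rather than validity.

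**2. Effect on the mean event count.** From the documents: n = 80. Assumed: a fraction f of patients is lost, and their mean count is R times that of those kept. Then full mean = kept mean × [(1 − f) + fR], so

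relative bias = 1/(1 + f(R − 1)) − 1.

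Example: f = 0.05, R = 3 gives 1/1.10 − 1 = −9.1%.

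| R | f = 2.5% (2 of 80) | f = 5% (4) | f = 10% (8) |
|---|---|---|---|
| 3 | −4.8% | −9.1% | −16.7% |
| 2 | −2.4% | −4.8% | −9.1% |
| 0.5 | +1.3% | +2.6% | +5.3% |
| 0 | +2.6% | +5.3% | +11.1% |

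R above 1 represents changes prompted by lows; R below 1 represents changes prompted by highs in patients with few lows.

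**3. Effect on the share with any event.** Shift = f(p − p_lost)/(1 − f). With an assumed true share p = 0.5, and all or none of those lost having events, the shift is ∓0.5f/(1 − f): 1.3, 2.6 and 5.6 points at the three values of f.

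**4. Sampling error for comparison.** For the share, 1.96 × √(0.25/80) = 11.0 points. For the mean count, under an assumed negative binomial with mean m and size k, the relative half-width is 1.96 × √(1/m + 1/k)/√80: 34.6% (k = 0.5, m = 2), 33.5% (0.5, 3), 21.9% (2, 2), 20.0% (2, 3).

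**5. Does the bias survive the narrower reading?** An illustrative simulation used gamma subject rates with the m and k above and Poisson events. Each event triggered a change with probability 2-5%, there was a 2% background chance of change over 14 days, and monitoring stopped at the change. Between 5.7% and 15.1% of patients were withdrawn. Bias in the mean rate:

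- all withdrawn patients dropped: about −4 to −27%;
- only those under 7 days dropped (3-8% of patients): about −2 to −18%;
- everyone kept, total events over total monitored time: about −1 to −12%;
- everyone kept, negative binomial with log wear-time offset: within about 0.5%, but down to about −4% if subject rates are lognormal;
- everyone kept, unweighted mean of subject rates: +15% or more, and unstable.

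In the reverse case, changes fell only in the lower half of hypoglycemia rates, with 5-10% withdrawn. Dropping withdrawn patients gave +2.5 to +9.9%, the pooled rate +1 to +5%, and the offset model +0.7 to +3.8%.

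**6. The two medication wordings.** Section 7 concerns the 12 weeks before entry and sets a threshold or requires a new drug. Section 16 concerns the monitoring period and sets no threshold, yet describes the change as meeting an exclusion criterion. The two do not match.

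**The case against.** Three objections carry weight.

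*Loss of data is not stated for every withdrawal.* A reader might infer that all readings from every withdrawn patient are discarded. The documents do not say so: the only stated exclusion from analysis is under 7 days of CGM, and a patient withdrawn on Day 10 could fairly be kept. This stands. Loss follows from the rules only for first-week changes and is otherwise unspecified.

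*The 7-day rule is a data-sufficiency rule.* Nothing in the documents links glycemia to short wear except early withdrawal. This stands too; the rule matters here because it is what turns an early withdrawal into an exclusion.

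*The route is narrow and every rate is assumed.* Monitoring lasts 14 days and Section 7 screens out recent regimen changes. Section 11 says "Subjects will be advised to return to the research site on Day 14 to remove the CGM device for analysis", and Section 19 offers results to the endocrinologist "if requested by the subject at the end of their participation". Events seen only on the sensor are therefore unlikely to prompt a change during monitoring. Events that patients notice still can. These features limit how often the problem arises, but they do not remove it.

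A reader might also infer that the plan will understate hypoglycemia. The documents do not support a direction: losing patients treated for lows pushes the estimate down, and losing patients treated for highs can push it up.

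**Conclusion.** The point holds in this form: as written, the rules exclude patients with a first-week medication change from a primary and safety endpoint that may itself have caused the change, and they leave later withdrawals undefined. The direction is unknown. The size cannot be fixed, because the documents give no event, change or withdrawal rates. In the illustrations the bias ranges from a few percent to more than a quarter of the mean count if all withdrawn patients are dropped, and stays inside the sampling error at n=80 in each simulated setting. It is thus plausibly within sampling error, but that judgement rests on assumed trigger rates. It should be fixed, with medium confidence, because the remedy is inexpensive and the selection would otherwise be invisible to a reader.

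**What to change.** 1. Limit the 7-day minimum and the medication-change exclusion to the analyses of HbA1c and fructosamine against mean glucose.
2. For hypoglycemia and hyperglycemia, use all retrievable CGM readings from every monitored subject, up to the medication change or the end of the sensor record, and say so in Sections 12 and 16.
3. Analyse events per monitored time. A count model with a log wear-time offset is one suitable choice; the pooled rate can be shown beside it. Avoid an unweighted mean of subject rates when there is no minimum wear.
4. Report withdrawals and exclusions by reason, and show results with and without withdrawn or short-wear subjects.
5. Reconcile the medication-change wording of Sections 7 and 16.

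**Cost.** Mostly wording, but not only that. Section 11 provides for sensor removal only on Day 14, so the plan must say how a withdrawn subject's sensor is retrieved and that the data may be kept. There will be a second analysis set and noisier data from short wear. Some bias remains, because stopping at an event-triggered change is informative; the offset model reduces it only as far as its assumed distribution of subject rates is right.
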